## **The current research status and development trends**

Akturk U (2018) proposed  the establishment of a multidisciplinary care intervention team comprising nurses, physicians, and psychological counselors. Prior to the implementation of the intervention, the psychological counselor should conduct comprehensive training for the entire team. During this phase, the team would collaboratively review and clarify the theoretical foundations of Swanson's theory, essential caregiving skills, and the psychological characteristics of patients. Based on this foundational work, an effective care framework and operational mechanism can be developed, ultimately enhancing the overall quality of patient care.

Health literacy serves as a critical foundation for delivering high-quality healthcare. Improving the health literacy of patients and caregivers can enhance the

efficiency and effectiveness of care delivery. According to the World Health Organization, individual health literacy encompasses the knowledge, motivation, and skills that enable individuals to access, understand, and apply health information and services in order to promote and sustain their health .

Swanson's theory was developed by the distinguished British professor Swanson. The theoretical framework is primarily inspired by three phenomenological studies . First, it explores which types of caregiving behaviors are most beneficial for pregnant women who have experienced unsuccessful childbirth. Second, it investigates the care requirements of new parents and the corresponding caregiving behaviors exhibited by caregivers. Finally, the theory establishes a caregiving model tailored for high-risk pregnant women—such as first-time mothers, single parents, and individuals with low educational attainment or socioeconomic status. Following the implementation of the intervention, these women demonstrated a significant improvement in their ability to care for their newborns.

[name] proposed that, with regard to care behaviors, caregivers should actively acquire an understanding of the identities of the service recipients, the methods of providing effective care, and the rationale behind their ongoing service provision. Furthermore, caregivers are expected to integrate multidisciplinary knowledge, including aspects of caregiving and humanistic concern .

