### **Research Plan, Technical Approach, Organizational Structure**

#### **4.1 Research Plan**

##### 1. Inclusion and exclusion criteria

The inclusion criteria were as follows: gestational age ranging from 28 to 36 weeks, stable vital signs for at least 24 hours, and parental accompaniment of preterm infants during hospitalization. The exclusion criteria included: preterm infants with severe congenital or genetic disorders, dysfunction of vital organs, or requiring mechanical life support; preterm infants requiring surgical intervention; and preterm infants with a birth weight below 500 grams.

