### 3. Outcome

The primary outcomes included the corrected head circumference, weight, and height of the newborns at 1 month, 3 months, and 6 months of age. Additionally, parental anxiety and depression status was assessed using the Trait Anxiety Inventory (T-AI), which measures long-term and stable anxiety tendencies, and the State Anxiety Inventory (S-AI), which evaluates current or recent anxiety states. Parental self-efficacy and satisfaction with their parenting role were assessed using the Child-Parental Self-Competence Scale (C-PSOC).

Secondary outcomes included the length of hospital stay, discharge weight, and the number of unplanned hospitalizations.

Confounding factors included fetal gender, gestational age, birth weight, duration of oxygen therapy, duration of total enteral feeding, and the duration required to

transition from full enteral feeding to full oral feeding, defined as the time from the initiation of oral feeding (when preterm infants begin to suck voluntarily and consume the first milk volume exceeding 5 mL) to the complete establishment of full oral feeding.

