#### 5. Statistical Analysis

Measurement data that conformed to a normal distribution were expressed as mean  $\pm$  standard deviation (SD). Independent sample t-tests and paired sample t-tests were employed to assess intergroup statistical differences. For measurement data that did not conform to a normal distribution, results were summarized as median (interquartile range), and the Mann-Whitney U test was applied to evaluate statistical differences between groups. Categorical data were presented as frequency and percentage [n (%)] and analyzed using the chi-square test. Repeated measurement data were examined using repeated measures analysis of variance (ANOVA). All statistical analyses were conducted using SPSS version 25.0.

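### The parental scales (S-AI, T-AI, C-PSOC) have no fixed respondent, no parent-level covariate among the six listed confounders, and no covariate-adjusted group comparison.

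*Combined protocol and SAP*

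**What the plan says.** All references are to the combined protocol and SAP, section 4.1 unless stated.

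- **Parent-measured outcomes (item 3, Outcome).** In the primary-outcome paragraph: "parental anxiety and depression status was assessed using the Trait Anxiety Inventory (T-AI") together with the S-AI, and "Parental self-efficacy and satisfaction with their parenting role were assessed using the Child-Parental Self-Competence Scale (C-PSOC"). The growth measures carry time points of 1, 3 and 6 months. The parental scales carry none of their own.
- **Listed confounders (item 3).** "Confounding factors included fetal gender, gestational age, birth weight, duration of oxygen therapy, duration of total enteral feeding", and a sixth, the duration of the "transition from full enteral feeding to full oral feeding, defined as the time from the initiation of oral feeding" to its full establishment.
- **Who the parent is (item 1, Inclusion and exclusion criteria).** Eligibility requires "parental accompaniment of preterm infants during hospitalization". No parent is specified. Items 2 to 5 speak only of parents, new parents, families or family members.
- **Analysis (item 5, Statistical Analysis).** "Independent sample t-tests and paired sample t-tests were employed to assess intergroup statistical differences". Mann-Whitney, chi-square and repeated measures ANOVA are also named. No test is given a covariate.
- **Background (The current research status and development trends).** The caring model is said to have been shaped for high-risk pregnant women such as "first-time mothers, single parents, and individuals with low educational attainment or socioeconomic status".

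**The concern.** The scales describe the parent who fills them in, and two things are left open.

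First, the respondent. Nothing says whether mother, father or both answer, or that one person answers throughout. Under item 2 the intervention guides parents in daily care and gives them psychological counselling, while control care is described as standard medical services. The person who completes the form could therefore differ by arm as a result of allocation. If the respondent changes between assessments, a within-family change score mixes a change in one person with a difference between two people. Paired tests and repeated measures ANOVA assume that this does not happen.

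Second, adjustment. A parent's role and whether this is a first child plausibly bear on parenting self-competence, but no parent characteristic is on the confounder list and no model would use one. A group difference on C-PSOC or S-AI then has no planned check against parent imbalance.

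These are two separate gaps; the missing respondent does not follow from the confounder list.

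**Working it through.** **1. Count from the text.** Listed confounders: infant sex, gestational age, birth weight, oxygen duration, total enteral feeding duration, time to full oral feeding. Six are listed, six are infant-level and none is parent-level. Statements fixing the respondent: none. Covariates named in item 5: none, so even the six infant factors enter no stated analysis.

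**2. The plan's own figure (item 4, Sample Size Calculation).** n = 2 × (1.96 + 0.84)² × 2.5 / 1.5² = 17.42, rounded up to 18 per group, as stated. The planned standardised effect is 1.5/√2.5 = 0.949 SD, and power at 18 per group is 81.2%. The outcome behind 2.5 and 1.5 is not named, so 18 per group serves below only as a working size.

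**3. Chance imbalance under random allocation.** Assume half of parents are first-time and let each arm be Binomial(18, 0.5).
- Gap of at least 4 parents (4/18 = 22 points): 24.3% of trials.
- Gap of at least 6 parents (6/18 = 33 points): 6.5% of trials.

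The same applies to the respondent's role. If the share of mothers answering is 50%, 70% or 80% (assumed), the arms differ by 20 points or more in 24%, 20% or 14% of trials.

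**4. Bias at a given imbalance.** Bias = gap × effect.
- First-time status, assumed effect 0.3 to 0.8 SD, gap 6/18: 0.10 to 0.27 SD.
- Respondent role, assumed mother-father difference 0.2 to 0.8 SD, gap 10 to 30 points: 0.02 to 0.24 SD, which is 2% to 25% of 0.949 SD.

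**5. Error rates.** Simulation of the unadjusted t-test, 18 per group, SD 1 within first-time and other parents, no treatment effect:
- Averaged over random allocation: about 5% for shifts of both 0.3 and 0.8 SD, because chance imbalance is already part of the standard error.
- Given a gap of exactly 6 parents: about 6% (0.3 SD) to 10% (0.8 SD).

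A noncentral t with SD fixed at 1 would overstate the upper value. First-time status also widens the pooled variance: with 12 of 18 against 6 of 18 it is about 1 + 0.8² × (12/18) × (6/18) × (18/17) = 1.15.

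**6. Precision gained.** For a 50/50 factor with shift d, R² = 0.25d² / (1 + 0.25d²).
- d = 0.3: 0.0225/1.0225 = 2.2%; equivalent n = 18/(1 − 0.022) = 18.4.
- d = 0.8: 0.16/1.16 = 13.8%; equivalent n = 18/(1 − 0.138) = 20.9.

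A baseline score can do more. If its correlation with follow-up is 0.3, 0.5 or 0.7 (assumed), the residual SD shrinks by √(1 − r²), and power for a 0.949 SD effect at 18 per group rises from 81.2% to 84.7%, 90.8% or 97.9%.

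**The case against.** Under random allocation the unadjusted t-test is valid, and a reader who infers an inflated error rate from the 6% to 10% figure would be wrong. That figure holds only given a gap of 33 points. This stands, and it limits the case for adjustment to precision and protection against chance imbalance.

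Other parts of the defence also stand:

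- Gestational age, birth weight and oxygen duration may well affect parental anxiety. The accurate statement is that no parent-level covariate is listed, not that no relevant one is.
- T-AI, "which measures long-term and stable anxiety tendencies", is a parent-level measure already planned. However, it is listed as an outcome, with no baseline time point and no place in a model.
- Every enrolled infant must have an accompanying parent, so both arms have one. That makes a difference in respondents between arms a possibility, not something the documents show. The requirement still does not say who answers, or that it is the same person each time.
- The background passage describes how the theory arose. It does not show that those traits predict scores in NICU parents. It only makes them reasonable candidates to record.

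One might also infer that education or first-time status will not be collected. The document contains no data-collection form or baseline list, so absence from a confounder list does not establish that.

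**Conclusion.** The point holds as a modest but real design gap. The confounder count and the absence of a named respondent are plain from the text. The respondent gap matters more, because later adjustment cannot cleanly repair a switch of respondent or a selection of respondents that depends on arm.

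The size of the adjustment benefit rests on assumed values: half of parents first-time, an effect of 0.3 to 0.8 SD, and 18 per group. On these, first-time status explains about 2% to 14% of variance, equivalent to about 18 to 21 per group. A claim of larger gains from parent covariates would need a further assumption that the documents do not supply.

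A reader might also infer that allocation is non-random and that large imbalances are to be expected. The sections reviewed do not state the allocation method, and no particular imbalance can be derived from them. If allocation is not random, adjustment would also reduce confounding, by an amount that cannot be given here.

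**What to change.** In section 4.1, item 3, name one responding parent per family before group assignment and use that parent at every assessment. State when the scales are given. Record at enrolment that parent's role (mother or father), first-time status, education and baseline scale scores.

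In item 5, replace the unadjusted t-test for S-AI and C-PSOC with a prespecified linear model (ANCOVA) containing group, the baseline score and a small set of parent covariates, for example role and first-time status.

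The cost is a few enrolment items, one baseline administration of the scales, and a sentence or two in each of items 3 and 5. Statistically it takes two or three degrees of freedom from the 34 available at the stated minimum of 18 per group (2 × 18 − 2). The covariate set should therefore stay short.

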#### 4. Sample Size Calculation

With the assistance of Select Statistical Services (<https://select-statistics.co.uk/calculators/sample-size-calculator-two-means/>), the sample size was determined. This calculation utilizes the following formula to compute the sample size  $n$ :

[figure not shown]
$$n = \frac{2 \times (Z_{\alpha/2} + Z_{\beta})^2 \times \sigma^2}{d^2}$$

Among them, " $Z_{\alpha/2}$ " denotes the critical value of the standard normal distribution at  $\alpha/2$  (for a 95% confidence level,  $\alpha = 0.05$ , and the corresponding critical value is 1.96); " $Z_{\beta}$ " denotes the critical value of the standard normal distribution at  $\beta$  (for a statistical power of 80%,  $\beta = 0.2$ , and the corresponding critical value is 0.84); " $\sigma^2$ " represents the population variance, which is set at 2.5; and "d" refers to the minimum detectable difference, which is set at 1.5 for the primary outcome analysis. Based on these parameters, the required minimum sample size per group is calculated to be 18 participants.

#### 5. Statistical Analysis

Measurement data that conformed to a normal distribution were expressed as mean  $\pm$  standard deviation (SD). Independent sample t-tests and paired sample t-tests were employed to assess intergroup statistical differences. For measurement data that did not conform to a normal distribution, results were summarized as median (interquartile range), and the Mann-Whitney U test was applied to evaluate statistical differences between groups. Categorical data were presented as frequency and percentage [n (%)] and analyzed using the chi-square test. Repeated measurement data were examined using repeated measures analysis of variance (ANOVA). All statistical analyses were conducted using SPSS version 25.0.

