##### 2. Intervention and Control

FICare nursing method guided by Swanson's caring theory encompasses the following five dimensions:

Understanding: A neonatologist provided a comprehensive explanation regarding the developmental progress of premature infants, potential complications, and essential aspects of nursing care to ensure the family gained a thorough understanding

of the care requirements for premature infants.

Accompaniment: Two nursing guides provided essential support to parents of newborns in the NICU, helping to alleviate the anxiety and sense of helplessness among family members and fostering a relationship of trust between the medical staff and the families.

Help: A neonatal nurse played a guiding role in facilitating parental involvement in the daily care of premature infants, which encompassed feeding guidance, introduction of complementary foods, skin care, and related aspects.

Empowerment: A psychological counselor was assigned to provide psychological counseling and guidance to new parents, offering appropriate emotional support and assisting them in accessing necessary social and professional resources.

Maintaining Confidence: A neonatologist and a nurse monitored neonatal development through outpatient visits and telephone follow-ups to encourage families to sustain their confidence in improving infant health outcomes and to support them in maintaining a positive outlook when facing challenges in caregiving.

The control group will continue to receive the traditional model of hospital care, encompassing standard medical services such as physical health monitoring and nutritional support.

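### Paired t-tests are listed for between-group differences, and growth at three visits goes to an unadjusted repeated measures ANOVA that in classical form drops infants with a missed visit; one baseline-adjusted mixed model is preferable, by a margin that depends on the loss pattern.

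*Combined protocol and SAP*

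**What the plan says.** All references are to section 4.1 (Research Plan) of the combined protocol and SAP.

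- **5. Statistical Analysis**, on normally distributed measurements: "Independent sample t-tests and paired sample t-tests were employed to assess intergroup statistical differences".
- The same section, on repeated data: "Repeated measurement data were examined using repeated measures analysis of variance (ANOVA"). It gives no model terms, covariates, missing-data method or deciding contrast.
- **3. Outcome**, on growth: "The primary outcomes included the corrected head circumference, weight, and height of the newborns at 1 month, 3 months, and 6 months of age". The same item says "Confounding factors included fetal gender, gestational age, birth weight, duration of oxygen therapy, duration of total enteral feeding", followed by the time taken to move to full oral feeding. None of these six factors reappears in the analysis section.
- **2. Intervention and Control**: "The control group will continue to receive the traditional model of hospital care". The comparison is with a separate group, and no matching is described.
- **4. Sample Size Calculation**: the formula is for two independent means, with a variance of 2.5 and a minimum detectable difference "which is set at 1.5 for the primary outcome analysis"; "the required minimum sample size per group is calculated to be 18 participants". No allowance for loss is stated.

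**The concern.** A paired t-test needs a pairing, and nothing in the plan links an infant in one arm to an infant in the other. If the authors meant change within each arm, which is the likelier intent, the sentence is misworded, and such tests do not estimate the effect of the intervention.

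The growth analysis matters more. Classical repeated measures ANOVA needs a full set of visits, so one missed visit discards that infant's other measurements. With a minimum of 18 per arm and no loss allowance, this costs power. If loss is related to earlier growth and differs by arm, it can also bias the difference in either direction. The plan names sex, gestational age and birth weight as confounders but leaves any chance imbalance in them uncorrected.

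**Working it through.** **Inputs from the plan.** Variance 2.5 (SD = √2.5 = 1.581), difference 1.5, two-sided α 0.05, power 80%, 18 per arm, three visits.

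**Assumptions.** The plan gives no loss rate, loss pattern or within-infant correlation ρ. I take ρ = 0.5, 0.7 and 0.9, a difference of 1.5 at every visit, and exactly 18 enrolled per arm.

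**1. The plan's own figure.** 2 × (1.96 + 0.84)² × 2.5 / 1.5² = 17.42, rounded up to 18. It reproduces. Noncentral-t power at 18 per arm is 79.0% for one visit.

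**2. Paired test across unmatched arms.** The noncentrality is unchanged but the degrees of freedom fall from 34 to 17. Power is 76.5% against 79.0%, and simulated type I error is about 5% for both tests.

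**3. Average group effect over three visits, no loss.** The between-group test in a complete-data repeated measures ANOVA equals a t-test on each infant's mean. SD of that mean = √(2.5 × (1 + 2ρ)/3) = 1.291, 1.414, 1.528. Power is 92%, 87% and 82%, and is nearly the same for the mixed model.

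**4. Loss of 10% at each visit, independent across visits.** Complete infants: 0.9³ = 0.729, or 13.1 of 18. Share of the measurements taken that is discarded: 1 − 0.9² = 0.19.

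**5. Nested dropout.** Families who leave do not return; 3.3%, 6.7% and 10% are missing at months 1, 3 and 6. Complete infants: 90%, or 16.2 of 18.

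Unadjusted power for the average effect (mixed model with covariance taken as known, 34 df):

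| Loss pattern | Method | ρ = 0.5 | ρ = 0.7 | ρ = 0.9 |
|---|---|---|---|---|
| Independent, 10% per visit | Complete-case ANOVA | 82% | 74% | 68% |
| | Mixed model | 91% | 86% | 81% |
| Nested, 10% by month 6 | Complete-case ANOVA | 89% | 83% | 77% |
| | Mixed model | 91% | 86% | 80% |

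The gap is 9 to 13 points under independent loss and 2 to 3 points under nested loss. A simulation of the independent pattern with the covariance estimated (REML, unstructured, Satterthwaite) gave 82/75/68% against 91/86/82%.

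**6. Baseline adjustment, taken separately.** Suppose covariates explain 20% of the variance of the three-visit mean. Its residual variance is then 0.8 × 2.5 × (1 + 2ρ)/3. With 13.1 complete infants per arm, a complete-case ANCOVA has about 89%, 83% and 77% power, which is 7 to 9 points above the unadjusted ANOVA with no mixed model involved. If the 20% refers instead to single-visit variance, the figures are about 92%, 85% and 77%.

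**7. Bias, as an illustration only.** Let equal shares of each arm be lost by month 6, at random in the intervention arm but only from below the month-1 median in the control arm. The retained control mean shifts by 0.798 × 1.581 × ((1 + 2ρ)/3) × k, where k = 0.1/0.9 = 0.111 at 10% loss and 0.2/0.8 = 0.25 at 20%. The shifts are 0.09 to 0.13 and 0.21 to 0.29, so a true 1.50 is estimated as 1.37 to 1.41 and 1.21 to 1.29. If the losses come from above the median, the same amounts are added. For scale, the standard error of the average effect at 18 per arm is 1.291/3 to 1.528/3, or 0.43 to 0.51.

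**The case against.** **The growth analysis is inferred.** The ANOVA sentence does not name growth, and the same section lists independent t-tests, which keep every infant seen at a given visit. This stands as a caveat. Growth is, however, the only outcome with a visit schedule ("at 1 month, 3 months, and 6 months of age"), so it is the natural object of that sentence.

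**The loss is overstated.** A reader might infer that the planned analysis will discard 27% of infants. That figure needs 10% missing at each visit, independently. Dropout without return is ordinary in a six-month follow-up and then costs 10%. The documents support neither rate nor pattern, so both must be shown.

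**The mixed model gets credit for the covariates.** Simulated power for an adjusted mixed model under independent loss is 95-88%. Setting this against 82-68% for an unadjusted complete-case ANOVA suggests a gain of 13 to 20 points, but two changes are mixed, and covariates can be added to the ANOVA as well. This objection stands in full.

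**The paired test does little harm.** This is correct: 2.5 points of power and no inflation of type I error. A reader might infer a false-positive problem; there is none. It is a wording correction.

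**Eighteen is a minimum, not planned enrolment.** This also stands. With more infants the power losses shrink.

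**The bias pattern is contrived.** It is, and at 10% loss the shift is well below one standard error. It shows that bias is possible and can go either way, not that it will occur.

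**Conclusion.** The point holds. The paired t-test is assigned to a comparison it cannot make. The repeated growth data go to a method that in classical form drops partly observed infants and, as written, ignores the plan's own confounders. A baseline-adjusted mixed model on all observed visits is the better primary analysis.

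The size is uncertain. Unadjusted power rises by 9 to 13 points if 10% of visits are missed independently, by 2 to 3 points if 10% drop out in a nested pattern, and hardly at all without loss. These figures assume 18 per arm, a constant difference of 1.5 and correlation 0.5 to 0.9. Adjustment adds a further gain that does not depend on the choice of mixed model. The documents do not support a claim that the planned analysis is invalid or will be materially biased. The readable text does not describe how infants are allocated, and the conclusion does not rest on it; if allocation is not random, missing adjustment would matter more.

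**What to change.** 1. Delete paired t-tests as a between-group method. If kept, label them as describing within-arm change.
2. Analyse each growth measure with one linear mixed model on all observed visits (SPSS MIXED, REML, unstructured covariance, Satterthwaite degrees of freedom), with group, visit, group-by-visit, sex, gestational age and birth weight.
3. Leave out the oxygen and feeding durations. They may accrue after the intervention starts, and adjusting for them could remove part of its effect.
4. Report missing visits by arm and reason, and keep the complete-case ANOVA as a sensitivity analysis.
5. Before analysis, state the deciding contrast and any multiplicity rule. Both are the sponsor's choice. At 18 per arm without loss, the average effect has 82-92% power against 79% for one visit if the difference is constant, but 48-62% against 79% at month 6 if it builds as 0.5, 1.0, 1.5. A multiplicity rule must also cover the parental scales if they are primary; a correction across the three growth measures alone would not.

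**Cost.** SAP wording only: the procedure is in the named software and the covariates are already listed. There are two downsides. The unstructured covariance has six parameters in a small trial; simulated type I error (ρ = 0.7, 10% independent loss) was 6.1% unadjusted and 4.0% adjusted, with a Monte Carlo standard error of about 0.7 points, so both are compatible with 5%. The model also relies on data being missing at random, which the data cannot verify.
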